7.2 RECORDING AND REPORTING OF ADVERSE EVENTS

7.2.1 Investigational procedures and treatment

AEs will be collected throughout the study from screening appointment until week 10. If an AE is reported by the patient, the relationship of the event to the study treatment or procedures should be assessed by the local PI, or a delegated sub-PI or nurse. The following information will be recorded for all AEs:

- Medical term of the AE (SNOMED CT terminology)
- Start date and date of resolution
- Seriousness
- Severity
- Study treatment action
- Outcome
- Relationship with the study treatment
- Expectedness

SADEs, SAEs, and USADEs should always be recorded in the eCRF and reported to the Sponsor using the Sponsor's SAE reporting form. Any SAEs that occur during the screening period that resulted from the administration of any study procedures and are unexpected, should also be reported. The form should be emailed to the Trial Manager ([contact]) within 24 hours of the site team becoming aware of the event. If the site does not receive an acknowledgement of the receipt of the report within 24 hours, they should immediately contact the Trial Manager by telephone.

The Sponsor should immediately inform the CI of any reported SAEs. The CI should review the SAE to confirm causality and expectedness.

The Sponsor should also report all serious adverse events, whether initially considered to be device related to the MHRA (Any SAEs which indicate an imminent risk of death, serious injury or serious illness, and which requires prompt remedial action for other subjects, shall be reported within two calendar days of awareness, any other SAEs shall be reported within seven calendar days). The REC should be notified of any related and unexpected SAEs within 15 days. Reports of related and unexpected SAEs in double-blind trials should be unblinded. Investigators should only receive information on the code-break if it is necessary for the safety of the patient.

SAEs should be followed-up until resolution or a final outcome. All follow-up information should be emailed to the Sponsor as soon as it becomes available. The SAE form and any email correspondence related to the SAE should be filed in the investigator site file and in the electronic Trial Master File.

7.3 REPORTING OF PREGNANCIES

Although according to the package information leaflet Enterosgel® can be used in pregnant women and are excluding any pregnant participants from the trial. Any women of childbearing potential should agree to use a medically accepted method of contraception while they are receiving study treatment (i.e. until the end of the open-label period). Should a participant get pregnant while the patient was receiving study treatment, the site should notify the Sponsor within 24 hours of becoming aware of the pregnancy, by emailing the Sponsor's pregnancy reporting form to the Trial Manager ([contact]).

In case of a pregnancy while receiving study treatment, a participant should be withdrawn from the study. The pregnancy should be followed for outcome and any adverse outcome of pregnancy should be assessed for causality to the study treatment received. Pregnancy is not considered an AE unless a negative or consequential outcome is recorded for the mother or child/foetus.

8. STATISTICS

8.1 SAMPLE SIZE CALCULATION

In a previous clinical trial of Mebeverine in the treatment of FAPD in children [30], the mean (SD) change from baseline in the Wong-Baker FACES Pain Rating Scale in the placebo arm was -1.2 (1.5). We consider that a 1-point larger reduction in the Enterosgel arm (a mean change from baseline of -2.2) would be clinically significant. The number of patients required to observe this difference with 80% power and α =0.05 is approximately n=130 (or n=65 per arm). We would increase the sample size to n=154 (77 per arm) to allow for 15% drop-outs.

8.2 STATISTICAL ANALYSES

This trial will be reported according to the CONSORT guidelines for clinical trials (Consolidated Standards Of Reporting Trials statement (http://www.consort-statement.org/) [31]. Primary data analyses will be based on the intention-to-treat principle. The per-protocol analyses will include children with 80% or greater treatment compliance. Recruitment and attrition rates will be calculated as percentages with 95% CIs. Percentage of patients completing the protocol will be reported and reasons for deviations/study withdrawal collected. Data will inform a power calculation for a definitive clinical and cost-effectiveness study. Descriptive sub analyses, if numbers allow, will be made based on specific FGID diagnoses.

All statistical analyses will be described in detail in the Statistical Analysis Plan.

8.2.1 Baseline data

All participant baseline data will be summarised descriptively overall and by trial arm both as randomised and as analysed in the primary analysis. No formal statistical comparisons will be undertaken. Continuous measures will be reported as means and standard deviations while the categorical data will be reported as counts and percentages.

8.2.2 Primary analysis

The primary outcome will be analysed using an analysis of covariance (ANCOVA) model with treatment assignment and the baseline Stomach Pain and Hurt score as a covariate. In addition, an adjusted ANCOVA model will be performed by including pre-specified covariates (study site, sex and age group) measured at baseline. The unadjusted and adjusted mean difference between two groups in the primary outcome, together with its 95% confidence intervals (CIs) will be calculated. In addition, subgroup analysis of the primary endpoint will be performed on the pre-specified covariates. Analysis of secondary continuous outcomes will be performed in a similar way.

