3.2 STUDY OUTCOME MEASURES

3.2.1 Primary Outcome Measure

Comparison of the change in mean daily Wong-Baker FACES Pain Rating Scale (limited to abdominal pain) during weeks 1-2 (initial observation phase) and the double-blind phase (week 3-6) recorded in the daily diary in the Enterosgel® versus the placebo arm.

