3.2.2 Secondary Outcome Measures

3.2.2.1 Double-blind and Open-label treatment phase

The secondary outcome measures in the Enterosgel® versus the placebo arm during the double-blind and open-label treatment phase are listed in **Table 1**.

Table 1. Secondary outcome measures for the double-blind and open-label treatment phase

Outcome Measure	Time points and method of assessment	Definition
1. Abdominal pain score	Daily diary	Mean daily Wong-Baker FACES Pain Rating Scale
2. Frequency of abdominal pain	Daily diary	Proportion of days with any abdominal pain
3. Days missed nursery/school	Daily diary	Proportion of days missed nursery/school
4. Change in the Stomach Pain and Hurt total score	Baseline, weeks 6 and 10 (PedsQL 3.0 GIS module; comprised of 6 items)	Parent/carer proxy-report for 3-4-year-olds and child self-report from 5-18 years; by parent/carer proxy-report for 3-18-year-olds)
5. Change in individual components of the PedsQL 3.0 GIS module	Baseline, week 6, 10 (PedsQL 3.0 GIS module)	Parent/carer proxy-report for 3-4-year-olds and child self-report from 5-18 years; by parent/carer proxy-report for 3-18 years old. Individual components of the PedsQL 3.0 GIS module: stomach discomfort when eating (5 items), food and drink limits (6), trouble swallowing (3), heartburn and reflux (4), nausea and vomiting (4), gas and bloating (7), constipation (14), blood in bowel movement (2), diarrhoea (7), worry about bowel movements (5), medicines (4), communication (5).
6. Change in total PedsQL 3.0 GIS module score	Baseline, week 6,10 (PedsQL 3.0 GIS module)	Parent/carer proxy-report for 3-4-year-olds and child self-report from 5-18 years; by parent/carer proxy-report for 3-18 years old.
7. Change in health-related quality of life KIDSCREEN- 27 questionnaire	Baseline, week 6, 10 (Health-related quality of life KIDSCREEN-27)	Total Health-related quality of life KIDSCREEN- 27 score (parent reported 3-7 years, child self- report 8-18 years)
8. Change in health-related quality of life KIDSCREEN-27 questionnaire "General Mood and Feelings about Yourself" sub- score	Baseline, week 6, 10 (Health-related quality of life KIDSCREEN-27)	Health-related quality of life KIDSCREEN-27 sub-score for "General Mood and Feelings about Yourself" (7 questions; parent reported 3-7 years, child self-report 8-18 years)
9. Acceptability of the study interventions	Daily (diary)	Compliance with taking study intervention each day*

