6.3.2 PedsQL-3.0-GIS

The Pediatric Quality of Life Inventory[™] (PedsQL[™]) Gastrointestinal Symptoms Module for patients is a questionnaire for patients with functional gastrointestinal disorders (FGIDs) and organic GI diseases, hereafter referred to as "GI disorders". The module consists of a patient self-report ages 5-18 and parent proxy-report for ages 2-18 years. PedsQL-3.0-GIS evaluates the intensity of symptoms during the previous one month period [2]. The modules are separated into age categories; teens (13-18yrs), child (8-12 yrs), young child (5-7yrs) and toddlers (2-4 years). It considers fourteen unidimensional scales measuring

ENT08UK Clinical Investigation Plan v1_07/05/2025

stomach pain, stomach discomfort when eating, food and drink limits, trouble swallowing, heartburn and reflux, nausea and vomiting, gas and bloating, constipation, blood, diarrhea, worry, medicines, and communication. The "worry about bowel movements" (5 questions) will be compared to study treatment effects on the intervention on anxiety/depression. Each question is scored on a scale from 0 to 4, and their sum is then calculated to obtain the total score. Higher scores indicate worse symptoms. Data suggests that the PedsQL-3.0-GIS has good measurement properties and can be used as a common metrics to compare GI-specific symptoms in clinical research and practice both within and across patient groups for FGIDs [27].

A copy of PedsQL-3.0-GIS is provided in Error! Reference source not found..

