8.2.3 Secondary analysis

Secondary outcome data will be summarised descriptively at each time point, overall and by trial arm. The secondary outcomes will be analysed either by comparing trial arms at week 6 using ANCOVA models adjusting for baseline scores, or by employing mixed effects models for repeated measurements (MMRMs). The baseline scores, treatment group, time point, and treatment group by timepoint interaction terms will be included as covariates. A random effect for participant will be used to account for repeated measurements within participants over time. This will allow efficient use of the data collected, and account for potential within patient correlation.

Further analysis with regards specific FAPD subgroup and ethnicity will also be undertaken and will be described in full in the formal statistical analysis plan [32,33].

ENT08UK Clinical Investigation Plan v1_07/05/2025

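### The primary ANCOVA adjusts the Wong-Baker change for the baseline of another instrument (PedsQL Stomach Pain and Hurt) and leaves out the weeks 1-2 Wong-Baker mean, which costs precision

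*Protocol*

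**What the plan says.** Section 3.2.1 of the protocol defines the primary outcome on the diary: "Comparison of the change in mean daily Wong-Baker FACES Pain Rating Scale (limited to abdominal pain) during weeks 1-2" against the double-blind weeks 3-6, compared between arms. Section 8.1 builds the sample size on the same scale.

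Section 8.2.2 analyses this outcome by ANCOVA with "treatment assignment and the baseline Stomach Pain and Hurt score as a covariate". A second version follows: "an adjusted ANCOVA model will be performed by including pre-specified covariates (study site, sex and age group) measured at baseline". Neither version mentions a Wong-Baker baseline.

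The named covariate comes from another instrument. Table 1 in section 3.2.2.1 lists "Change in the Stomach Pain and Hurt total score" as secondary outcome 4, with the source given as "PedsQL 3.0 GIS module; comprised of 6 items". Table 4 places the first PedsQL completion at week 0, and section 6.3.2 states that "PedsQL-3.0-GIS evaluates the intensity of symptoms during the previous one month period". The score therefore describes the month before the observation phase.

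For secondary outcomes, section 8.2.3 compares arms at week 6 "using ANCOVA models adjusting for baseline scores", or uses repeated-measures models that also contain baseline scores. Section 8.2.2 ends by saying that secondary continuous outcomes are handled much like the primary.

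**The concern.** In an ANCOVA of a change score, the covariate that matters most is normally the baseline of the same measure. It removes the part of the change that is regression to the mean. A different scale, taken earlier and over another recall window, can do this only in part.

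The right covariate is already collected. Inclusion criterion 5 in section 4.1 requires at least 11 of 14 diary days, so each eligible randomised child has a weeks 1-2 mean. Minimisation (section 5.1.1.1) uses centre, sex and age group, so nothing in the allocation balances baseline pain.

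Two things are at stake: the standard error of the main result, and how far that result moves when the arms happen to differ in baseline Wong-Baker score.

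**Working it through.** **Inputs from the protocol (section 8.1).** SD of change 1.5, difference 1 point, α 0.05 (taken as two-sided; sidedness is not stated), 80% power, 65 per arm evaluable, 77 per arm after 15% drop-out.

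**The plan's own figure.** n per arm = 2(1.96 + 0.842)² × 1.5² / 1² = 35.3, so 36 (37 by the exact t-test), not 65. The drop-out step does reproduce: 65/0.85 = 76.5, so 77. With SD 1.5, 65 per arm gives 96.7% power; 65 would be the 80% answer if the SD were about 2.03. That discrepancy is a separate matter. It is used here only to bracket the effect on power.

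**Assumptions.** Let ρ be the correlation between baseline and treatment-phase Wong-Baker, a that between PedsQL and baseline Wong-Baker, and b that between PedsQL and treatment-phase Wong-Baker. The SD σ is equal in both periods. The protocol gives none of these. The main case takes b = aρ, meaning that PedsQL predicts follow-up only through baseline Wong-Baker.

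**Residual variance of the change**
- No covariate: 2σ²(1−ρ)
- PedsQL (planned): 2σ²(1−ρ) − σ²(a−b)²
- Wong-Baker baseline: σ²(1−ρ²)

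With b = aρ, the ratio planned/own baseline is 1 + (1−ρ)(1−a²)/(1+ρ). At ρ = a = 0.5 this is 1 + 0.5 × 0.75/1.5 = 1.25.

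**Chance imbalance.** The planned estimate moves by −[(1−ρ) − a(a−b)] per point of baseline imbalance; with b = aρ this is −(1−ρ)(1−a²). Holding the SD of change at 1.5 gives σ = 1.5/√(2(1−ρ)). A 1-SE imbalance at 65 per arm is σ√(2/65). At ρ = a = 0.5, σ = 1.5, the imbalance is 0.263 points, and 0.375 × 0.263 = 0.10 point remains.

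Each cell gives the variance ratio, then the points left by a 1-SE imbalance:

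| ρ | a = 0.3 | a = 0.5 | a = 0.7 |
|---|---|---|---|
| 0.3 | 1.49; 0.14 | 1.40; 0.12 | 1.27; 0.08 |
| 0.5 | 1.30; 0.12 | 1.25; 0.10 | 1.17; 0.07 |
| 0.7 | 1.16; 0.09 | 1.13; 0.08 | 1.09; 0.05 |
| 0.8 | 1.10; 0.08 | 1.08; 0.06 | 1.06; 0.04 |

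**Simulation check.** In 10,000 trials with 65 per arm, ρ = a = 0.5 and a true effect of −1, the mean estimate was −1.00 under every model. The SE was 0.257 with PedsQL and 0.230 with the own baseline (variance ratio 1.25). The slope of the estimate on baseline imbalance was −0.51 with no covariate, −0.38 with PedsQL and −0.01 with the own baseline.

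**A wider SD.** Take SD 2.0 in each period, a = 0.5 and b = 0.35. At ρ = 0.5 the residual variances are 4 − 0.3² = 3.91 (planned) and 4 × 0.75 = 3.00 (own baseline), a ratio of 1.30. The 1-SE imbalance is 2.0 × √(2/65) = 0.351, and a(a−b) = 0.075. The shift is (1 − ρ − 0.075) × 0.351: 0.08 at ρ = 0.7, 0.15 at 0.5 and 0.18 at 0.4.

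**Power at 65 per arm, ρ = a = 0.5.** With SD of change 1.5, power is 97.5% under the planned model and 99.2% with the own baseline. With SD 2.03 it is 82.5% and 89.9%.

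**The case against.** Most of the case against concerns consequence, and most of it stands.

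- *Bias.* A reader might infer a biased primary result. Randomisation keeps the estimate unbiased. The outcome already subtracts baseline, so an imbalance does not pass through whole. Only the regression-to-the-mean remainder is left, with reversed sign.
- *Power.* A reader might infer an underpowered trial. Section 8.1 uses the unadjusted SD of change, and apart from one degree of freedom a baseline covariate can only help against that.
- *Size.* It is tempting to quote a shift of (1−ρ)σ√(2/65), or 0.10-0.21 points at SD 2.0. That is the formula for a change score with no covariate; with PedsQL in the model it is 0.08-0.18. Also, SD 2.0 with ρ = 0.5 implies an SD of change of 2.0, against 1.5 in section 8.1. With σ = 2.0, reaching 1.5 needs ρ = 1 − 2.25/8 = 0.72. The own baseline then saves only about 10.5% of the variance: planned 2.25 − 0.09 = 2.16, own 4(1 − 0.72²) ≈ 1.93.
- *Spread.* The closing sentence of 8.2.2 might suggest that the mismatch extends to the secondary outcomes. Section 8.2.3 points the other way: its baseline scores are naturally read as each outcome's own. The two sections need aligning, but the text does not show that the error spreads.
- *SAP.* Section 8.2 leaves detail to the SAP, which is not at hand. This objection does not stand, because the protocol itself names the covariate. An SAP that follows it carries the mismatch forward; one that departs from it contradicts the protocol on the primary analysis.

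PedsQL could be the better covariate only if |a − b| exceeded 1 − ρ, for example a gap of more than 0.5 at ρ = 0.5. That is implausible for a score taken before both diary periods.

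**Conclusion.** The mismatch is real and nothing else in the protocol corrects it: the primary Wong-Baker change is adjusted for a secondary outcome's baseline, and its own baseline is in no primary model. The harm is lost efficiency and avoidable sensitivity to chance imbalance, not bias and not power below the stated 80%.

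The planned estimate has about 6-49% more variance than one adjusted for the weeks 1-2 Wong-Baker mean, and 25% more at ρ = a = 0.5. A 1-SE imbalance at 65 per arm leaves roughly 0.1 point at an SD of change of 1.5, or 0.08-0.18 at SD 2.0 per period, against a 1-point target. The direction holds under any plausible correlations. The size rests on assumed values that the protocol does not supply. This is a should-fix point.

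**What to change.** In section 8.2.2, replace the PedsQL covariate with the mean daily Wong-Baker score over weeks 1-2, in both the main and the adjusted model. The PedsQL baseline may stay as an additional covariate; if so, state whether the child or the parent report is used at ages 5-18, since Table 1 lists both. Reword the closing sentence of 8.2.2 to agree with 8.2.3, so that each secondary continuous outcome is adjusted for its own baseline. The SAP should carry the same wording.

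The cost is a sentence or two in the protocol and SAP, with no new data and no change to the sample size. The change should be made before unblinding, so that the choice of covariate cannot look data-driven.

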5. INTERVENTIONS AND STUDY DEVICE

5.1 INTERVENTION

5.1.1 Treatment allocation

5.1.1.1 Double-blind phase

For the double-blind treatment phase, patients will be randomised in 1:1 ratio using a computer-based randomisation tool (Sealed Envelope Ltd, UK) to:

Control Group: will receive placebo daily for 4 weeks

Interventional Group: will receive Enterosgel® daily for 4 weeks

Randomisation will be based on the minimisation method where treatment allocation will be stratified by study centre, sex and age group (15-18 years; 7-14 years and 3-6 years). Minimisation allocates subjects to the treatment group that best maintains balance in stratifying factors. It is effective even at small sample sizes and with multiple stratification variables [24].

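### The first-listed primary ANCOVA leaves out the minimisation factors (centre, sex, age group), and no sentence names which of the two primary models decides superiority

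*Protocol*

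**What the plan says.** Protocol 5.1.1.1 sets the allocation: "Randomisation will be based on the minimisation method where treatment allocation will be stratified by study centre, sex and age group", with age bands 3-6, 7-14 and 15-18 years and a 1:1 ratio.

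Protocol 8.2.2 then sets the primary analysis in three steps:

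- The first model: "The primary outcome will be analysed using an analysis of covariance (ANCOVA) model with treatment assignment and the baseline Stomach Pain and Hurt score as" [...]. That score is its only covariate; centre, sex and age group are not in it.
- The second model: "In addition, an adjusted ANCOVA model will be performed by including pre-specified covariates (study site, sex and age group) measured at baseline". Its extra covariates are exactly the three minimisation factors.
- The reporting: "The unadjusted and adjusted mean difference between two groups in the primary outcome, together with its 95% confidence intervals (CIs) will be calculated".

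No sentence in 8.2.2 says which of the two estimates decides the superiority objective in 2.2.1. Section 8.2 leaves detail to a statistical analysis plan, which is not at hand, but the content of both models is already fixed in the protocol. Section 8.2.2 also carries the same approach over to the secondary continuous outcomes.

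**The concern.** Minimisation makes the arms alike on centre, sex and age group, so these factors contribute little to the chance difference between arms. A model without them still counts the outcome variation they explain as residual error. Its standard error then overstates the real uncertainty of the treatment difference. The confidence interval covers more than 95% of the time and the test rejects too seldom under the null.

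The analysis that matches the design is in the protocol, but it stands second. With both differences reported for one primary outcome and neither labelled as decisive, a reader cannot be certain beforehand which interval settles the question if the two fall on either side of the significance limit.

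**Working it through.** **Inputs.** From 8.1: difference 1 point, SD 1.5, α = 0.05 (two-sided assumed; the protocol does not say), 80% power, 65 per arm evaluable, 77 per arm enrolled. From 5.1.1.1: three minimisation factors, 1:1. Not in the documents, so assumed over a range: R², the share of outcome variance left after the baseline covariate that centre, sex and age group explain.

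**The plan's own sample size.** n per arm = 2(1.96 + 0.8416)² × 1.5² / 1² = 35.3, so 36, not 65. The dropout step does reproduce: 65/0.85 = 76.5, so 77 per arm and 154 in total. At SD 1.5, 65 per arm gives about 96.7% power; 80% power at 65 per arm corresponds to an SD of about 2.03. This mismatch is a separate matter. Here it means only that power is shown at two anchors.

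**Formulas, with the factors balanced by design.**

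- Overstatement of the standard error: 1/√(1−R²)
- True size of the nominal 5% test: 2[1 − Φ(1.96/√(1−R²))]
- Power without the factors: Φ((λ − 1.96)/√(1−R²))
- Power with the factors: Φ(λ/√(1−R²) − 1.96)

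Here λ is the difference divided by its standard error before the factors are used. At the 80% design point λ = 1.96 + 0.8416 = 2.8016. At SD 1.5, λ = 1/(1.5√(2/65)) = 3.80.

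Worked case, R² = 0.10: √0.90 = 0.9487. The SE ratio is 1/0.9487 = 1.054. Size is 2[1 − Φ(2.066)] = 0.039. At the 80% point, power is Φ(0.8416/0.9487) = 81.2% without the factors and Φ(2.8016/0.9487 − 1.96) = 84.0% with them; the gap is 2.7 points before rounding.

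| Assumed R² | SE too large by | True size | Power at 80% point, without / with | Power at SD 1.5, without / with |
|---|---|---|---|---|
| 0% | 0% | 5.0% | 80.0 / 80.0% | 96.7 / 96.7% |
| 5% | 2.6% | 4.4% | 80.6 / 82.0% | 97.1 / 97.4% |
| 10% | 5.4% | 3.9% | 81.2 / 84.0% | 97.4 / 98.0% |
| 15% | 8.5% | 3.4% | 81.9 / 86.0% | 97.7 / 98.5% |

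**Check by simulation.** 4000 trials per setting, N = 130, SD about 2.03, minimisation on three factors with an assumed 0.8 biased coin. The Monte Carlo error of a 5% rate is √(0.05 × 0.95/4000) = 0.0034.

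| R² | Type I error without | Type I error with |
|---|---|---|
| 0 | 0.048 | 0.049 |
| 0.05 | 0.048 | 0.054 |
| 0.10 | 0.037 | 0.046 |
| 0.20 | 0.038 | 0.058 |
| 0.30 | 0.021 | 0.048 |

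The direction agrees with the formulas. Single entries are noisy: at 0.20 both rates lie above the formula values of 0.028 and 0.050, but the gap between them (2.0 points) is close to the predicted 2.2. At R² = 0.10 the model without the factors reports a mean standard error of 0.357 against a true spread of 0.339, about 5% too large.

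**How often the two models disagree.** At R² = 0.10 under a true 1-point difference, 79.75% of trials reject without the factors, 82.88% with them and 83.05% with at least one. They therefore split in (83.05 − 79.75) + (83.05 − 82.88) = 3.5% of trials. Under the null the rates are 3.68%, 4.60% and 4.68%, a split in 1.00 + 0.08 = 1.1%.

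**The case against.** The strongest reply has four parts.

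- **The lead model can be inferred.** Section 8.2.2 states one ANCOVA for the primary outcome and introduces the other as an addition. A reader might infer from the two reported estimates that the trial has no defined answer. The text does not support that: the order and wording point to the model without the factors. What stands is that the hierarchy is left to inference and that, on the natural reading, the lead is the model that does not match the allocation.
- **The factors are not ignored.** The adjusted model is pre-specified with exactly the right covariates, so it cannot be invented after the data are seen. This stands, and it reduces the problem to which estimate leads.
- **The size rests on an assumed R².** One may expect faces-scale ratings to differ between ages 3 and 18, but that concerns their level. The primary outcome is each child's own change, with a baseline covariate besides, and age differences in level need not carry into change. This stands. Zero belongs in the range, and at zero nothing is lost.
- **The harm is small and in the safe direction.** A reader might infer a material loss of power or a risk of a false superiority claim. Neither follows. Without the factors, power stays at or above the 80% target, and at the stated SD the loss is 0.3 to 0.8 points for R² of 5 to 15%. Under the null the test rejects less often than 5%, not more. In the simulation, even counting a rejection by either model added at most about 0.1 point to the adjusted model's type I error.

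That a statistical analysis plan could name the lead is also fair. But a plan that followed 8.2.2 as written would inherit the weaker lead, and one that reversed the order would depart from the protocol.

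**Conclusion.** The point holds as a modest matter of efficiency and labelling. The protocol minimises on centre, sex and age group, lists first a primary model that omits them, and does not say outright which estimate decides. If the factors explain 5 to 15% of the remaining variance, the first model's interval is 2.6 to 8.5% too wide and its true size is 4.4 to 3.4%. The power forgone is 1.4 to 4.0 points at an 80% design point and under 1 point at the stated SD of 1.5 with 65 per arm. If they explain nothing, there is no cost. A positive result from the first model would remain valid.

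These figures rest on the assumed R², on minimisation achieving near balance, and on a two-sided 5% test. The case for the change lies less in the size of the gain than in its being almost free and leaving one deciding estimate.

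**What to change.** In Protocol 8.2.2, name one primary analysis that decides superiority: the ANCOVA with treatment, the baseline covariate, study centre, sex and age group (3-6, 7-14, 15-18 years). Label the model without the minimisation factors a sensitivity analysis. Apply the same order to the secondary continuous outcomes, which 8.2.2 ties to this approach. Which baseline score should serve as the covariate is a separate point and is not settled by this change.

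The cost is one sentence and four degrees of freedom (centre 1, sex 1, age group 2) with about 130 evaluable children. All three factors are already recorded for allocation, so no new data are needed.
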